11.2.1.2 CONTROL TEST SITE

The subject will rest their arm on a comfortable surface and be instructed to keep their eyes closed throughout the duration of the test. On the subject's left forearm, one inch from the crook of their elbow, with a washable marker, a 1 inch by 1 inch square box is to be drawn and a dot placed in the middle of the box. Using the filaments, and starting with the smallest filament, stimulation will be applied from a 90 degree angle to the dot, not exceeding 1 second of stimulation. With each application of stimulation, inform the subject you will be touching them by saying "now". The subject should respond yes or no to feeling the touch. The results are to be recorded on MDT Data Collection Form.

11.2.1.3 PAIN SITE

For this test, the subject is to wear a hospital gown so that their bare back and affected site can be seen. The subject will be asked to bend forward keeping their legs straight and to touch their toes. The Research Assistant will locate the apex of the curve. On the right side of the apex, a 10 cm dot from the middle of the back will be made. The subject may then sit down for the test. The subject will be asked to keep their eyes closed throughout the test. Using the filaments, and starting with the smallest filament, stimulation will be applied from a 90 degree angle to the dot, not exceeding 1 second of stimulation. With each application of stimulation, the subject will be informed that you will be touching them by saying "now". The subject should respond yes or no to feeling the touch. Record results on MDT Data Collection Form.

During the test, periodically (once every 3-4 times) the patient should be presented with a "false positive" by saying "now" without touching their skin. If the subject says they felt the touch, report this as a false positive on the collection form.

Between each stimulus, the filament is put down even if even if repeating the same stimulus.

11.2.1.4 MDT DETAILED TEST PROCEDURE

Procedure - Descending

This test procedure should be followed for both the control and pain test site.

1. Begin at filament (1g) (higher if the subject does not feel this force) on marked location.
2. If the subject feels the filament, present the next thinner filament, (0.6g). Continue to present thinner and thinner filaments until the subject no longer detects the touch.
3. Record the LAST DETECTED FORCE in grams (the filament above the one the subject did not feel).

Procedure - Ascending

4. Begin with the filament that was noted as last detected force, and begin moving up to next thicker filaments, augmenting the force each time.
5. Continue until the subject feels the touch again.
6. Note the FIRST DETECTED force in grams.
7. Repeat the descending and ascending procedures for a total 3 times of each.

NOTE: If the subject does not feel the initial (1g) filament, move up 3 filaments (e.g. 4g). Keep repeating this until the patient feels the touch. Then proceed with the protocol using the newly selected filament.

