9 STUDY INFORMATION

9.1 BASELINE VISIT

The expected duration for the patient's participation in the research is 6 months and will consist of a baseline visit, In-hospital visit, 6 week post-op visit and a 6 month post-op visit.

At the baseline visit, the subject will be expected to complete the following:

- ✓ Pain intensity rating (self-reported) (Wong Baker Faces Pain Scale)

- ✓ Medical History Interview (Patient History Collection Form)
- ✓ Approximately 10 mL of blood will be drawn and blood pressure will be taken
- ✓ Quantitative Sensory Testing (QST = MDT/PPT/CPM tests)

The subject will be expected to fill out the following questionnaires:

- ✓ Pain numerical rating scale for children (Baseline - 4 questions)
- ✓ State-Trait Anxiety Inventory (STAI-C)
- ✓ Pain Catastrophizing Scale (PCS-C)
- ✓ Functional Disability Index (FDI)
- ✓ Revised Children Anxiety and Depression Scale (RCADS)
- ✓ Pittsburg Sleep Quality Index (PSQI)
- ✓ Neuropathic Pain Questionnaire (DN4)
- ✓ Tampa Scale for Kinesiophobia (TSK)
- ✓ Scoliosis Research Society (SRS-30)
- ✓ Adolescent Pediatric Pain Tool (APPT)

The visit should take approximately 1 hour

Once the subject's CPM results from the baseline visit have been assessed, the subject will be categorized into one of two arms: 1) Sub-optimal endogenous inhibitory response or 2) Optimal endogenous inhibitory response. The sub-optimal group will then be randomized to either Clonidine or the placebo, and the optimal group will be also randomized to either Clonidine or the placebo.

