11.2.1.1 DATA COLLECTION AND TOUCH TEST SENSORY EVALUATOR PREPARATION

The Research Assistant will start by entering the required information on the MDT Data Collection Form, as well as setting up the 5 TouchTest Sensory Evaluators (filaments) that will be used during testing (1g, 0.6g, 0.4g, 0.16g, 0.07g). The Research Assistant will demonstrate the procedure using the subject's palm of their hand.

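### The ascending MDT run starts at a filament the subject has just felt, so it can never read below the descending run; separately, the starting filament is stated in two contradictory ways

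*Combined protocol and SAP*

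**What the plan says.** Section 11.2.1.1 lays out five filaments "that will be used during testing (1g, 0.6g, 0.4g, 0.16g, 0.07g"), so 1 g is the thickest and 0.07 g the thinnest. Section 11.2.1 gives a wider available range, 0.008 to 300 g.

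Section 11.2.1.4 sets out the runs:

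- **Descending.** "Begin at filament (1g) (higher if the subject does not feel this force) on marked location". Step down until a filament is missed, then "Record the LAST DETECTED FORCE in grams (the filament above the one the subject did not feel").
- **Ascending.** "Begin with the filament that was noted as last detected force, and begin moving up to next thicker filaments". Step 5 continues until the subject feels touch again, and step 6 notes the first force detected.
- Each run is done three times. No rule is given for turning the six readings into one value.
- **Scope.** "This test procedure should be followed for both the control and pain test site".

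The site descriptions in 11.2.1.2 (control site) and 11.2.1.3 (pain site) use the same sentence as each other: "Using the filaments, and starting with the smallest filament, stimulation will be applied from a 90 degree angle to the dot".

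Section 9.1 defines the baseline sensory testing as "Quantitative Sensory Testing (QST = MDT/PPT/CPM tests"). The study plan table schedules MDT at seven time points: baseline, surgery, in-hospital days 1, 2 and 5, six weeks and six months. Section 16.4 plans a secondary repeated-measures analysis of change in QST.

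**The concern.** Pairing a descending with an ascending run is useful when each run can err in either direction. Here the ascending run begins at the value the descending run has just produced. If that filament is felt on re-presentation, the ascending reading repeats the descending one; if it is missed, the reading is higher. A lower reading is impossible.

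The wording also leaves room for two practices. Step 4 can mean presenting the felt filament again, or going straight to the next thicker one. Step 5 speaks of feeling touch again, which presupposes a start at a filament that was not felt, so it does not settle the matter.

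The smallest-filament wording in 11.2.1.2 and 11.2.1.3 is a different problem. It gives the opposite starting end from 11.2.1.4 for the same test at the same two sites. Two assistants, or one assistant at two visits, could each follow the text and run the test differently. In a measure taken seven times and analysed for change, that adds avoidable variation.

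**Working it through.** The documents state no figure that depends on the MDT procedure, so there is nothing to reproduce. The check is logical first, then numerical.

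**1. Logic.** Let D be the descending reading (last filament felt) and A the ascending reading (first filament felt going up). The ascending run starts at D and only increases, so A ≥ D in every pair.

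**2. A consistent responder, by hand.** Suppose everything at or above 0.5 g is always felt and everything below is always missed. Descending: 1 g felt, 0.6 g felt, 0.4 g missed, so D = 0.6 g.

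- Felt filament presented again: A = 0.6 g. Combined value √(0.6 × 0.6) = 0.600 g.
- Straight to the next thicker filament: A = 1 g. Combined value √(0.6 × 1) = 0.775 g.
- Start at the first unfelt filament (0.4 g): missed, then 0.6 g felt, so A = 0.6 g. Combined value 0.600 g.

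The first reading adds no shift. The second adds 0.775 / 0.600 − 1 = 29%. With a threshold of 0.4 g the second reading gives √(0.4 × 0.6) / 0.4 = 1.22, a 22% shift.

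**3. A variable responder, by simulation.** The following assumptions are not in the documents:

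- detection probability is cumulative normal in log10 force, with spread s of 0, 0.1, 0.2 or 0.3;
- the true 50% threshold is 0.25, 0.4, 0.5 or 0.8 g;
- there are no false alarms;
- filaments above 1 g are 1.6, 2.5, 4 g and upward, and none is thinner than 0.07 g;
- the six readings are combined by geometric mean.

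There were 6,000 simulated subjects with three pairs each in every scenario. Columns 3 to 5 give the combined value divided by the true threshold.

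| True (g) | s | Felt filament again | Next thicker | First unfelt | Again ÷ unfelt | Next ÷ unfelt |
|---|---|---|---|---|---|---|
| 0.25 | 0 | 1.60 | 1.96 | 1.60 | 1.00 | 1.22 |
| 0.25 | 0.3 | 1.82 | 2.17 | 1.58 | 1.15 | 1.37 |
| 0.4 | 0 | 1.00 | 1.22 | 1.00 | 1.00 | 1.22 |
| 0.4 | 0.3 | 1.63 | 1.96 | 1.44 | 1.13 | 1.36 |
| 0.5 | 0 | 1.20 | 1.55 | 1.20 | 1.00 | 1.29 |
| 0.5 | 0.3 | 1.57 | 1.86 | 1.38 | 1.14 | 1.35 |
| 0.8 | 0 | 1.25 | 1.58 | 1.25 | 1.00 | 1.26 |
| 0.8 | 0.3 | 1.49 | 1.77 | 1.32 | 1.13 | 1.34 |

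The scenarios with s = 0.1 and 0.2 fall within the same ranges. Across all 16:

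- As written, A < D never occurs. With a start at the first unfelt filament it occurs in 0% of pairs at s = 0, and in about 4% to 42% at s = 0.1 to 0.3.
- If the felt filament is presented again, A = D in 62% to 100% of pairs. If staff go straight to the next thicker filament, A = D never occurs.
- Some upward deviation from the true threshold usually remains with the unfelt start (ratios 1.32 to 1.58 at s = 0.3). The start rule is not its only source.

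**4. Start-filament conflict.** In the same simulation, an ascending run begun at the smallest filament gave combined values equal to or lower than those of the rule as written (felt filament presented again). The as-written value was 0% to about 27% higher. The smallest-filament instruction therefore does not push thresholds up; it makes the procedure ambiguous.

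**The case against.** Several points on the other side stand.

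- **Size.** A 15% shift is small beside the filament spacing. Adjacent forces in the set differ by 50% (0.4 to 0.6 g) to 150% (0.16 to 0.4 g). For a perfectly consistent responder, with the felt filament presented again, the shift is zero.
- **Information.** A reader might infer that the ascending runs are worthless. They are not. In a further simulation (assumed population median 0.25 g), the rank correlation with the true threshold at noise 0.25 and between-subject SD 0.15 was 0.717 for descending runs alone, 0.767 for all six as written, and 0.787 with the unfelt start. The written rule delivers 0.050 of a possible 0.070 gain. At noise 0.05 and SD 0.30 the values were 0.953, 0.961 and 0.969.
- **Reach.** A reader might infer that the primary objective is undermined, because section 6 makes pre-operative QST the predictor and 9.1 counts MDT within QST. But section 6 describes the QST as assessing descending inhibition, 8.1 forms the groups from CPM, 16.5 defines its comparisons by inhibitory response, the primary endpoint in 16.1 is pain intensity, and no model in 16.4 names MDT.
- **Arms.** The same procedure applies to every subject, so nothing in the documents points to a bias between clonidine and placebo.
- **Precedence.** Section 11.2.1.4 is the detailed procedure and claims both sites, so it plausibly governs. That is a reasonable guess, but the documents do not state it, and the site sections still instruct the opposite.

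What remains is a run that can err in one direction only, a step 5 that does not match step 4, and an unreconciled start rule.

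**Conclusion.** The point holds as a fault in the test procedure, with limited reach. That the ascending reading cannot fall below the descending one follows from the text alone.

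The size does not follow from the text. It is 0% to about 15% in the combined threshold if the felt filament is presented again, and about 22% to 37% if staff move straight to the next thicker one, each relative to a start at the first unfelt filament. These ranges rest on the assumed detection curves, filament series and geometric-mean scoring.

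Two stronger conclusions are not supported. The conflicting start filament does not bias thresholds upward; it can add variation between operators or visits. And correcting the ascending start would not remove all upward deviation from the true threshold, since part of it remains under either rule.

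The consequence is reduced accuracy and reproducibility of MDT in the secondary repeated-measures analysis. It is worth correcting because the measure is collected seven times per patient and the change is a few words.

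**What to change.** In 11.2.1.4, change step 4 so that the ascending run begins at the first filament not felt in the descending run. Step 5 then reads correctly. If 0.07 g is felt, continue down with thinner filaments from the 0.008 to 300 g range in 11.2.1 until one is missed.

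Remove the smallest-filament start from 11.2.1.2 and 11.2.1.3, so that the start in 11.2.1.4 applies at both sites and all visits.

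The cost is a wording change to the procedure and the data collection form, with thinner filaments at hand. Values from patients already tested will not be fully comparable with later ones, so record the procedure version with each MDT result. Stating how the six readings are combined, for example by geometric mean, would be a useful optional addition but is not part of the error.

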11.2.2. PRESSURE PAIN THRESHOLD WITH JTECH ALGOMETER

The JTech Algometer should be connected to the pressure reading device using the 1cm probe. Ensure the mark on the subject's left forearm is still visible and the area is clean. The procedure will be explained to the subject and the test will be demonstrated to them on the palm of their hand. The test is to be performed on the control site and pain site.

Procedure

1. Turn on the Pressure Reading Device and note the test number down on the data collection sheet.
2. Apply the pressure device to the subject's previously designated areas that were used for MDT testing. Ensure you watch the device read out as you are applying pressure.
3. Begin to slowly increase pressure at a rate of ~1 N/s.
4. Stop when the subject says "STOP" and immediately write down the read out of the force (in N) displayed on the pressure device screen on your data collection form that was indicated when the patient said stop.
5. Wait 1 minute between each trial.
6. Repeat this procedure 3 times on the left upper forearm (control site) and on the subject's affected site (pain site).
7. Review the device's readings of the test and transcribe them to the MDT Response Form.

11.2.3 QUANTATIVE SENSORY TESTING (QST) THERMAL

The Research Assistant is to set up all required equipment.

1. Set up Chiller and water bath.
2. Set up Laptop with Software, Q-Sense and CoVAS, Thermode.
3. Ensure CoVAS is calibrated.
4. Ensure Q-Sense has performed its calibration test.
5. Ensure new subject file is created in software and is ready for testing.
6. Ensure CPM response form is ready to be completed.

11.2.3.1 INSTRUCTIONS FOR THE SUBJECT

The following instructions are to be explained to the subject prior to starting the study tests.

11.2.3.2 COVAS (COMPUTERIZED VISUAL ANALOG SCALE)

The Research Assistant will explain the CoVAS device to the subject. The CoVAS device is a sliding scale which is connected to the laptop's software. The subject is instructed to use the scale slider to indicate the intensity of their pain on a scale of 0 to 10. It is important that the subject understand that this device will not control the temperature of the test.

11.2.3.2.1 UNPLEASANT FACTOR OF PAIN

The Research Assistant will describe various experiences or sensations the subject will feel throughout the test. The subject needs to understand the temperature will continue to increase – going from warm to hot, then to a point they will feel pain, and eventually to the point it will be too painful at which point they should stop the test. The subject should be instructed to indicate – “warm” as they feel the increase in temperature; “pain” due to the heat, and “stop” when it is too painful.

11.2.3.2.2 RELATIONSHIP BETWEEN COVAS AND UNPLEASANT FACTOR OF PAIN

The Research Assistant will describe the correlation of the pain the subject is experiencing to their indication of it on the CoVAS scale – thus rating their pain on the scale from “0” being no pain at all to “10” being worst pain tolerable.

11.2.4 QST THERMAL FAMILIARIZATION PRE-TEST

1. Set up the new subject in the software on the laptop; fill out the required information and save it.
2. Select the program “Pain Threshold Pretest”, select (Hand Palmer Middle). This test will be used to explain and familiarize the subject with the procedure, to demonstrate how hot the Thermode will get and how to use the COVAS device to assess their pain intensity. It is important that the patient understands that as soon as they say “stop”, the temperature will decrease immediately. The Thermode has a cut off temperature of 50 degrees.
 - Place the Thermode on the palm of the subject's hand. Start the pre-test. The subject should indicate three things to the Research Assistant – that the Thermode is “warm”, that it's “painful” and finally “stop” when it is too painful to continue. If the subject understands the test, repeat the test and ask them to rate their pain intensity on the CoVAS throughout the test. If the subject does not understand the test, repeat the test.
 - Record the subject's Threshold for pain and Threshold for Tolerance on the CPM response form.

11.2.4.1 QST THERMAL VAS50% DETERMINATION PRE-TEST

Once the patient understands, move to New Test and change the body site to “Forearm Medial” and save the changes. The forearm “pre-test” is used to determine the temperature corresponding to the patient’s VAS50%. The pain and threshold tolerance temperatures are also noted.

- Place the Thermode on the subject’s forearm approximately 1 inch below the crook of their elbow. Start the pre-test. The subject should indicate three things to the Research Assistant – that the Thermode is “warm”, that it’s “hot” and finally “stop” when it is too painful to continue. The subject will rate their pain intensity with the CoVAS throughout the test. If the subject seems to not understand the test, or the Research Assistant feels there was an issue with the test, repeat the test.

Once the Thermode Pre-Test is successfully completed, proceed to the Thermode Test.

11.2.4.2 THERMODE TEST BEFORE BATH

The Research Assistant will prepare the Software for the Thermode Test. The subject’s VAS50% score will be used to personalize the Thermode Test.

1. For the Thermode test, the subject’s “Left Forearm Medial” will be used. Select the site just below the site used for the pre-test.
2. This Thermode Test is for a duration of 2 minutes and the temperature remains at the subject’s VAS50% temperature throughout. Although the temperature remains constant at the subject’s VAS50%, the subject is instructed that the temperature will vary throughout the test. The subject should indicate their pain intensity with the COVAS device with “0” being no pain at all and “20” being the worst pain imaginable. Assistant feels there was an issue with the test, repeat the test.
3. The pain threshold, VAS50% and the pain tolerance should be recorded on the CPM response form.

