11.2.4.4 THERMODE TEST AFTER BATH

For the Thermode test, the subject's "Left Forearm Medial" will be used. Select the site just below the site used for the previous test.

This Thermode Test is for another duration of 2 minutes and the temperature remains at the subject's VAS50% temperature throughout. Although the temperature remains constant at the subject's VAS50%, the subject is instructed that the temperature will vary throughout the test. The subject should indicate their pain intensity with the CoVAS device with "0" being no pain at all and "10" being the worst pain tolerable. If the Research Assistant feels there was an issue with the test, repeat the test.

The pain threshold and the pain tolerance should be recorded on the CPM response form.

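### The before-bath heat test is rated 0–20 with one top anchor, while the after-bath test and the CoVAS instructions use 0–10 with another, and nothing reconciles them

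*Combined protocol and SAP*

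**What the plan says.** Section 11.2.3.2 introduces the CoVAS as one slider wired to the laptop ("The CoVAS device is a sliding scale which is connected to the" software) and tells the subject to "indicate the intensity of their pain on a scale of 0 to 10". Section 11.2.3.2.2 adds the anchors: "0” being no pain at all to “10” being worst pain tolerable".

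The forearm pre-test in 11.2.4.1 is "used to determine the temperature corresponding to the patient"'s VAS50%, again with CoVAS ratings: "The subject will rate their pain intensity with the CoVAS throughout the test". That temperature is then held for two minutes in each of two heat tests.

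- **Before the bath (11.2.4.2):** CoVAS, "0” being no pain at all and “20” being the worst pain imaginable".
- **After the bath (11.2.4.4):** CoVAS, same duration and temperature, at a site just below the earlier one, with 0 as no pain and "10' being the worst pain tolerable".

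Sections 8.1, 9.1 and 10 use the baseline result to class each subject as optimal or sub-optimal and randomise within those classes. Section 16.5 builds its two listed comparisons on the same classes.

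**The concern.** CPM asks whether pain from one stimulus falls when a second painful stimulus is applied elsewhere. A before-and-after comparison of heat ratings answers that only if both are on one scale with one meaning at the top. As written, they are not.

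The following depend on the result:
- the meaning of the two strata;
- comparison 1 in 16.5 (sub-optimal versus optimal, placebo patients only), which is not randomised and rests wholly on the classification;
- the population of comparison 2 (clonidine versus placebo in sub-optimal patients);
- CPM repeated on Day 5 (9.3) and at six weeks and six months (9.5).

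Routine checking may not reveal a problem. The critical-data check in 15.2 confirms that QST was completed, not which scale was used.

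**Working it through.** The plan gives no figure for this point, so the check is a side-by-side reading followed by short arithmetic.

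**1. The rating instructions**

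| Section | Step | Range | Top anchor |
|---|---|---|---|
| 11.2.3.2 | CoVAS introduction | 0–10 | not stated |
| 11.2.3.2.2 | CoVAS anchors | 0–10 | tolerable |
| 11.2.4.1 | VAS50% pre-test (CoVAS) | not restated | not restated |
| 11.2.4.2 | Heat test before bath (CoVAS) | **0–20** | **imaginable** |
| 11.2.4.3 | Verbal rating in bath | 0–10 | tolerable |
| 11.2.4.4 | Heat test after bath (CoVAS) | 0–10 | tolerable |

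The before-bath test is the only outlier, and it differs in both range and anchor. No section rescales it.

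**2. What reaches the data**

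Section 11.2.4.2 lists what goes on the form: "The pain threshold, VAS50% and the pain tolerance should be recorded on the CPM response form". Section 11.2.4.4 lists threshold and tolerance. Neither lists the CoVAS rating, so it presumably comes from the software. The export unit is not stated.

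**3. Three cases, taking CPM as the percent change between the two heat ratings (an assumption)**

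Let b be the before rating and a the after rating.

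- *Case 1: 0–10 'tolerable' was used in practice.* Both ratings are on one scale, so equal pain gives 5/10 to 5/10 = 0%. There is no error.
- *Case 2: the software stores slider position.* Half the slider to half the slider is 0%, so the numeric range drops out. The anchor difference remains, and the documents give neither its size nor its sign.
- *Case 3: raw b on 0–20 is compared unscaled with raw a on 0–10.* Ignoring any anchor effect:
  - true change = (a/10)/(b/20) − 1 = 2a/b − 1
  - apparent change = a/b − 1 = 0.5 × (true change) − 0.5
  - no true change (a = b/2): apparent = 0.5 × 0 − 0.5 = **−50%**, whatever b is
  - a true 10% reduction: apparent = 0.5 × (−0.10) − 0.5 = **−55%**

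Case 2 is more plausible than case 3, given one slider wired to the software. Nothing in the documents supports case 3, but the unstated export unit means it is not excluded.

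**The case against.** **It is a typing slip.** Probably so. The sentence that follows in 11.2.4.2 is broken where 11.2.4.4 has it whole, and every other rating step that states a range uses 0–10. But a slip in one number would not also change the anchor. Staff working from this section would give subjects a different upper anchor from the one they had just been taught.

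**The CPM formula is inferred.** This stands. Section 4 describes CPM only in general terms, and no section says how the two heat tests are combined or where optimal ends. Any effect on strata is therefore conditional. The missing formula and cut-off are a separate point.

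**A uniform error would largely cancel.** This stands in part. If case 3 applied to everyone and CPM were percent change, the distortion is linear. Subject ranking, a median split and between-group test statistics for CPM would be unchanged, and differences would halve. A fixed cut-off would not be protected, nor would mixed practice. A point-difference definition would not be protected either: the error is then (a − b) − (a − b/2) = −b/2, which varies with the before rating.

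**Stronger readings.** A reader might infer that almost every subject would be classed as optimal. That would need a CPM formula, a cut-off and a spread. The only benchmark, a 10% reduction in section 4, is background from healthy subjects and is not stated as this trial's rule. A reader might also assume a before rating of 10 out of 20 because the test runs at VAS50%. That temperature comes from a rising-heat pre-test, and nothing says a constant two-minute stimulus is rated at half scale.

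**Conclusion.** The texts conflict in the current procedure, in range and in anchor; confidence in that is high. Followed as written, and with CPM taken as the change between the two heat ratings, the ratings are not on one scale. The size ranges from nothing (case 1), through an anchor effect of unknown size and sign (case 2), to a spurious 50% reduction when there is no true change (case 3).

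A reader might conclude that strata were misassigned or that the treatment comparison is compromised. The documents show neither. Confidence that any stratum was affected is low. The primary endpoint in 16.1 is a separate 0–10 numerical rating of average pain over seven days and is untouched. Clonidine versus placebo within a stratum remains a randomised comparison however the stratum was formed. What is exposed is the meaning of the strata, comparison 1 and follow-up CPM. This should be fixed, chiefly because the test defines the groups and the correction is cheap.

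**What to change.** 1. Check the testing script and the software export for the range and anchor actually used.
2. Align 11.2.4.2 with 11.2.3.2.2 and 11.2.4.4, so that both heat tests use 0–10, worst pain tolerable, for all further testing.
3. For subjects already tested, act on what the check shows:
   - **0–10 'tolerable' throughout:** record that and stop.
   - **Only the numeric range differed:** halve the before-bath ratings. Keep strata as randomised for clonidine versus placebo. Repeat comparison 1 with strata recomputed from the rescaled values, as a sensitivity analysis.
   - **The anchor differed for some subjects:** flag them and repeat comparison 1 without them, as a sensitivity analysis.
   - **The anchor differed for all:** report it as a limitation of the CPM measure. Rescaling cannot remove it, and excluding those subjects would leave nobody.

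The cost is one corrected line and one check. Rescaling, flagging and a repeat of one comparison are needed only if the check finds a departure. No visits or tests are added.
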